6.2 Definition of Dose-Limiting Toxicity

DLT Definition: A DLT is defined as any Grade 3 or greater AE that is assessed as related to at least 1 study treatment that occurs during the DLT Assessment Period (DLT exceptions are defined below). The DLT period during the phase 1 study will be 4 weeks from the first infusion of Hu5F9-G4 (magrolimab) (priming infusion). To be assessable for a DLT, patients must have

NCI Protocol #: 10384

Version Date: September 5, 2023

received at least three infusions of Hu5F9-G4 (magrolimab), two infusions of mogamulizumab, and completed four weeks of assessment, or else have experienced a DLT anytime after receiving the priming dose of Hu5F9-G4 (magrolimab). Patients unable to receive the planned treatment during the four weeks due to treatment-related adverse events will also be considered to have experienced a DLT.

DLT Exceptions: The following are exceptions to the DLT definition and will NOT be considered a DLT:

- Grade 3 anemia; however, Grade 3 hemolytic anemia is considered a DLT.
- Grade 3 hyperbilirubinemia that resolves to \leq Grade 2 with supportive care within 1 week and is not associated with other clinically significant consequences.
- Transient Grade 3 nausea, vomiting, diarrhea, local reactions, influenza-like symptoms, myalgias, fever, headache, acute pain, or skin toxicity that resolves to \leq Grade 2 within \leq 72 hours after medical management (e.g., supportive care, including immunosuppressant treatment) has been initiated.
- Grade 3 fatigue that resolves to \leq Grade 2 within 1 week on study.
- Grade 3 magrolimab-related infusion reactions in the absence of an optimal pretreatment regimen, which is defined as acetaminophen or a comparable non-steroidal anti-inflammatory agent, plus an antihistamine and corticosteroids.
- Grade 3 electrolyte disturbances (hyperkalemia, hypophosphatemia, hyperuricemia, etc.) that resolves to \leq Grade 2 or baseline within 1 week.
- Grade 3 or 4 lymphopenia or grade 3 leukopenia not associated with other clinically significant consequences.
- Transient (\leq 48 hours) Grade 3 fatigue, local reactions, flu-like symptoms, fever, headache, nausea, emesis, and diarrhea.
- Other single laboratory values out of normal range that have no clinical correlate, and resolve to Grade \leq 1 or to baseline within 7 days with adequate medical management.
- Tumor flare phenomenon defined as local pain, irritation, or rash localized at sites of known or suspected tumor.

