- Grade 3 rash, erythroderma, skin pain or photosensitivity that resolves to \leq Grade 2 within 1 week with adequate medical management. Grade 4 rash or any grade Stevens-Johnson syndrome or toxic epidermal necrolysis will be considered DLTs.

Management and dose modifications associated with the above adverse events are outlined in Section 7.

Dose de-escalation will proceed within each cohort according to the following scheme (Figure 7) (Hong *et al.*, 2019). Dose-limiting toxicity (DLT) is defined above.

[figure not shown]

Figure 7: Phase 1b Dose De-escalation Design

Six patients will be enrolled at dose level 1 of 30mg/kg Hu5F9-G4 (magrolimab) and 1mg/kg mogamulizumab. If ≤ 1 DLT is observed in the initial 6 patients, then dose level 1 will be selected as the RP2D. If 2 DLTs are observed in the initial 6 patients, then an additional group of 3 patients will be enrolled at dose level 1. If there are no DLTs in this 3 patient group, then dose level 1 will be selected as the RP2D. If at any point there are >2 DLTs seen at dose level 1, then this dose level will close, and 6 patients will be enrolled at the new dose level -1: 20mg/kg Hu5F9-G4 (magrolimab) and 1mg/kg mogamulizumab. If ≤ 1 DLT is observed in the initial 6 patients, then dose level -1 will be selected as the RP2D. If 2 DLTs are observed in the initial 6 patients, then an additional group of 3 patients will be enrolled at dose level -1. If at any point there are >2 DLTs seen at dose level -1, then the trial will be stopped for unacceptable toxicity. It is believed that further reductions below a dose of 20mg/kg would not achieve adequate target occupancy for Hu5F9-G4 (magrolimab).

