6.4 Duration of Therapy

In the absence of treatment delays due to adverse event(s), treatment may continue for 12 cycles or until one of the following criteria applies:

- Disease progression. Patients randomized to the mogamulizumab-only arm may crossover as per section 6.6. Relapse in skin or blood compartments as defined by the response criteria is not considered progression and does not require removal from the treatment protocol.
- Intercurrent illness that prevents further administration of treatment
- Unacceptable adverse event(s)
- Patient decides to withdraw from the study
- General or specific changes in the patient's condition render the patient unacceptable for further treatment in the judgment of the investigator
- Clinical progression
- Patient non-compliance
- Pregnancy
 - All women of child bearing potential should be instructed to contact the investigator immediately if they suspect they might be pregnant (e.g., missed or late menstrual period) at any time during study participation.
 - The investigator must immediately notify CTEP in the event of a confirmed pregnancy in a patient participating in the study.
- Termination of the study by sponsor
- The drug manufacturer can no longer provide the study agent

The reason(s) for protocol therapy discontinuation, the reason(s) for study removal, and the corresponding dates must be documented in the Case Report Form (CRF).

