
*It is recommended to perform skin biopsies when possible with molecular T-cell receptor clonality studies to help distinguish rash from progressive disease
 
** Magrolimab may be held at the investigator's discretion for up to 2 weeks from the time of the scheduled infusion for grade 3 rash. Patients requiring a magrolimab delay of >2 weeks from their scheduled infusion should go off protocol therapy. Upon restarting magrolimab after a delay, there will be no dose reduction.
 
*** Mogamulizumab may be held up to 4 weeks from the time of the scheduled infusion for grade 2-3 rash. Patients requiring a mogamulizumab delay of >4 weeks from their scheduled infusion should go off protocol therapy. Upon restarting mogamulizumab after a delay, there will be no dose reduction.
		

Recommended management: High potency topical steroids may be used for grade 2-3. Subjects should apply topical steroids only to areas of suspected rash and avoid areas of known lymphoma disease and should try to reduce topical steroids to medium or low potency as tolerated. For grade 2, systemic corticosteroids may be given. For grade 3, systemic corticosteroids should be given. A dose of 40mg prednisone daily or equivalent is suggested. If systemic corticosteroids are given, efforts should be made to taper as tolerated to a dose of 10mg prednisone daily or equivalent.
		

All Other Drug-related Toxicity***	Management/Next Dose for Hu5F9-G4 (magrolimab) and Mogamulizumab
Grade 3	Hold ** until \leq Grade 2.
Grade 4	Off protocol therapy

* Patients with intolerable or persistent Grade 2 drug-related AE may hold study medications for up to 2 weeks at physician discretion.
 
**Patients requiring a delay of >2 weeks should go off protocol therapy.
 
*** Lymphopenia and/or leukopenia are the pharmacologic effect of mogamulizumab and will not be considered an AE for this study. However, neutropenia will be considered an AE and managed as above.
	

All Other Drug-related Toxicity***	Management/Next Dose for Hu5F9-G4 (magrolimab) and Mogamulizumab
---	---

Dosing interruptions are permitted in the case of medical/surgical events or logistical reasons not related to study therapy (e.g., elective surgery, unrelated medical events, patient vacation, and/or holidays). Patients should be placed back on study therapy within 2 weeks of the interruption. The reason for interruption should be documented in the patient's study record.

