Interim Safety Analysis: Before proceeding to the Phase 2 study, the Phase 1b will report satisfaction of the DLT safety criteria and provide a complete report of adverse events and a listing of patients in the Phase 1b that were taken off treatment due to adverse events, and the cycles in which that occurred. During the Phase 2 study, a formal amendment will be considered if at any point the first course DLT rate exceeds 30%, inclusive of all Phase 1b/2 patients treated at the RP2D on the combination of Hu5F9-G4 (magrolimab) and mogamulizumab, and accrual will be held pending review. Additional toxicity monitoring rules beyond cycle 1 follow:

The grade 3-4 AE rate of mogamulizumab throughout multiple cycles of the MAVORIC study was 41% (75 of 184 patients), with 28/184 stopping for AE (15%). The median PFS was approximately 7.7 months. Two of the three on-treatment deaths with mogamulizumab single agent (sepsis and polymyositis) were considered treatment related (2 of 184).

The optimistic scenario is that the combination of Hu5F9-G4 (magrolimab) and mogamulizumab will have enhanced activity over single agent mogamulizumab offsetting the potential increased toxicity of the doublet over single agent mogamulizumab ab. It is expected that the toxicity will be higher with the doublet, and this will be further amplified if the combination is active, keeping patients on treatment longer and increasing the chance of cumulative toxicities and sporadic toxicities. As a result, the rules for toxicity monitoring throughout the study will trigger a Toxicity Monitoring Committee (TMC) meeting (members of the TMC will receive the report at the time of the trigger and will respond within two weeks of the report of the trigger) to decide upon further action based on the totality of the data on both arms. The Toxicity Monitoring Committee will have the authority to hold study accrual and will send a report to the Data Coordinating Center, which will also be reviewing severe adverse events and the totality of the data at the regularly scheduled intervals (every 6 months) [separate from the monthly data coordination center review of data]. The Toxicity Monitoring Committee will consist of the NCI drug monitor, the NCI disease monitor, the study PI and the site PI/treating physician, or the respective designees for the toxicity committee members.

The triggering rules for Toxicity Monitoring Committee are as follows:

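### The tumor-flare DLT exception has no grade or time limit, so prolonged Grade 3 rash or pain on lesional skin can be left out of the Phase 2 safety counts

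*Combined protocol and SAP*

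**What the plan says.** Section 6.2 defines a DLT as a related event of Grade 3 or worse in the assessment period, then lists exceptions. Two of them meet on the skin:

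- **Flare:** "Tumor flare phenomenon defined as local pain, irritation, or rash localized at sites of known or suspected tumor". Nothing is said about grade, duration or confirmation.
- **Rash:** "Grade 3 rash, erythroderma, skin pain or photosensitivity that resolves to" Grade 2 or lower within one week. The same bullet adds "Grade 4 rash or any grade Stevens-Johnson syndrome or toxic epidermal necrolysis will be considered DLTs".

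The section does not say which applies when both fit. It does add a clause on missed dosing: "Patients unable to receive the planned treatment during the four weeks due to treatment-related adverse events will also be considered" to have had a DLT.

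Two Phase 2 rules in section 9.1 (Interim Safety Analysis) depend on this definition:

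- **First-course hold:** accrual is held pending review, and an amendment considered, "if at any point the first course DLT rate exceeds 30" percent. It counts Phase 1b and Phase 2 patients given the combination at the RP2D.
- **Between-arm comparison:** events meeting DLT criteria, at any time on treatment, are compared at 28 and 56 patients with one-sided alpha 0.15, of which 0.044 is spent at the first look.

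**The concern.** The one-week limit shows that the authors meant a Grade 3 rash that does not settle to count as a DLT. The flare bullet allows the same event to be exempted because of where it sits. In most tumors that overlap would be small. Here it may not be: section 2.1.1 describes MF as a disease of skin lesions and SS as generalized erythroderma. Section 2.3.1 reports rash and drug eruption as the most common events of Grade 3 or worse with mogamulizumab in its pivotal trial, with 7% discontinuing.

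Two sites could classify the same rash differently and both be following the protocol. The safety rules that use DLT criteria would then run on a lower count than the rash bullet intends. Phase 1b is complete, but the definition remains in use through the two Phase 2 rules.

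**Working it through.** **1. The two bullets side by side (treatment-related event on lesional skin)**

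| Event | Rash bullet | Flare bullet | Outcome |
|---|---|---|---|
| Grade 3 rash or skin pain, at Grade 2 or lower within 1 week | exempt | exempt | exempt, no conflict |
| Grade 3 rash or skin pain, longer than 1 week | not exempt, so a DLT | exempt | unresolved |
| Grade 4 rash, SJS, TEN | expressly a DLT | exempt only if read alone | best read as a DLT, though this is not stated |

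The gap is the middle row.

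**2. The plan's figure for the between-arm rule**

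Inputs from section 9.1: 14 then 28 patients per arm; control 41%, doublet 62%; stated chance of triggering above 70%. The plan does not name the test statistic, so a z-test of two proportions is assumed.

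- Look 1 boundary: upper 0.044 point of the normal = 1.706.
- Look 2 boundary: solves P(Z1 ≥ 1.706 or Z2 ≥ c) = 0.15 with correlation √(28/56); c = 1.095.
- Variance term: 0.41×0.59 + 0.62×0.38 = 0.4775.
- Expected z: 0.21/√(0.4775/14) = 1.14 at look 1; 0.21/√(0.4775/28) = 1.61 at look 2.
- Trigger probability: 70.8% (pooled variance 69.5%; exact binomial with pooled z 67.1%).

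The stated figure is reproduced by the normal approximation.

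**3. What exempted events would do to that probability**

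The documents give no rate of prolonged Grade 3 lesional rash, so the losses below are assumptions shown as a range (normal approximation; exact values in brackets where given).

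| DLT-criteria events lost to the flare label | Trigger probability |
|---|---|
| None | 70.8% (67.1%) |
| 2 points, doublet only | 65.1% (61.4%) |
| 5 points, doublet only | 56.2% (52.6%) |
| 10 points, doublet only | 41.2% (38.2%) |
| 15 points, doublet only | 27.7% (25.6%) |
| 2 to 15 points, equal in both arms | 70.7% to 72.9% |
| 5% to 15% of events, same share in both arms | 67.8% to 62.2% |

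Equal losses do almost nothing. The same share lost in each arm takes more events from the arm with more events and costs a little. Only a clear imbalance matters much.

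**4. The plan's worked examples**

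Pooled z = (p_D − p_C)/√(2p̄(1−p̄)/n).

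| Control v doublet | z | Boundary | Triggers |
|---|---|---|---|
| 5/14 v 10/14 | 1.89 | 1.706 | yes |
| 5/14 v 9/14 | 1.51 | 1.706 | no |
| 4/14 v 9/14 | 1.89 | 1.706 | yes |
| 11/28 v 16/28 | 1.34 | 1.095 | yes |
| 11/28 v 15/28 | 1.07 | 1.095 | no |
| 10/28 v 15/28 | 1.34 | 1.095 | yes |

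The plan's examples sit at the minimum doublet counts that trigger, so removing any one doublet event, for whatever reason, removes the trigger. Removing one from each arm does not.

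**5. The 30% hold**

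This rule counts combination patients only, so no control arm offsets an exempted event. Each one lowers the observed rate by 1/N: for example, 5 percentage points at N = 20. The starting point is the 1 of 6 from Phase 1b.

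**The case against.** The exceptions form a list in which meeting any one bullet is enough, so overlap is normal and needs no precedence rule. Grade 3 fatigue falls under two bullets, and skin toxicity settling within 72 hours sits beside the one-week rash bullet. Grade 3 anemia and lymphopenia also have no time limit. On this view the flare exemption is a choice, not an oversight. That is a fair reading, but it confirms that prolonged Grade 3 lesional rash is exempt, which defeats the one-week limit in the very next bullet for this disease.

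Other safeguards exist and they stand, in part:

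- The missed-treatment clause catches some cases, but only in the first four weeks and only if dosing is missed. Holding for Grade 3 rash is optional: magrolimab at the investigator's "discretion for up to 2 weeks from the time of the scheduled infusion for grade 3 rash", and, also by discretion, "Mogamulizumab may be held up to 4 weeks from the time of the scheduled infusion for grade 2-3 rash".
- The early-stopping trigger covers doublet patients who stop for adverse events before the third cycle, while "treatment may continue for 12 cycles".
- The treatment-related-death trigger does not use DLT criteria and is unaffected.
- The six-monthly Data Coordinating Center review, the DSMB (section 9.6) and the twice-yearly external DSMC (section 14) see the wider data, without a numeric rule for this event.

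Four stronger readings are tempting, and the documents do not support them:

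- *Grade 4 rash, SJS or TEN escapes the definition.* The specific sentence naming them is best read as governing.
- *The flare label will be used often.* Section 12.1.4 says only that lesions may look worse early, and it concerns pseudoprogression in response assessment, not adverse-event classification. Section 7 recommends biopsy to separate rash from progression.
- *The between-arm comparison is biased.* Both arms receive mogamulizumab, the drug the documents link to rash. The magrolimab risk list in section 10.1 puts maculo-papular rash among events with insufficient evidence of causation. No reason is given to expect more flare labels in one arm.
- *The one-event reversals show a fragile rule.* They follow from choosing minimum triggering counts as examples.

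**Conclusion.** The point holds as a minor gap in a safety definition. As written, treatment-related Grade 3 rash or skin pain on lesional skin lasting more than one week can be exempted as flare although the adjoining bullet counts it. It can then be missing from the 30% first-course hold and, if labelling differs between arms, from the between-arm comparison.

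The size is unknown because the frequency of such events is not given. The trigger probabilities above rest on assumed losses, an assumed z-statistic and, for the doublet-only rows, an imbalance for which the documents give no evidence. The first-course hold does not need that imbalance, since it counts only combination patients. The documents do not say whether any Phase 1b event was classed as flare, so nothing here shows that the recommended dose was wrongly chosen.

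**What to change.** In section 6.2:

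1. Limit the flare exception to Grade 3 events that return to Grade 2 or lower within one week, the limit already used for rash.
2. State that the sentence on Grade 4 rash, SJS and TEN applies at any site, including lesional skin.
3. State that both apply identically in the two arms.

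Then re-check the six Phase 1b patients under the revised wording, because the 30% rule pools them with Phase 2 and the rate should rest on one definition.

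If the sponsor wants flare exempt without limit, leave section 6.2 as it is and add a sentence to section 9.1: DLT-criteria counts go to the Toxicity Monitoring Committee with and without flare-labelled events.

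The cost is a few sentences and a review of six completed records. Alpha, boundaries and sample size do not change. Some prolonged true flares will count as DLTs, and the triggers may fire slightly more often. If the re-check found a second Phase 1b DLT, the sponsor would have to address it, since section 6.2 calls for three more patients after 2 in 6.

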6.3 General Concomitant Medication and Supportive Care Guidelines

Because there is a potential for interaction of Hu5F9-G4 (magrolimab) and mogamulizumab with other concomitantly administered drugs, the case report form must capture the concurrent use of all other drugs, over-the-counter medications, or alternative therapies. The Principal Investigator should be alerted if the patient is taking any agent known to affect or with the potential for drug interactions. The study team should check a frequently-updated medical reference for a list of drugs to avoid or minimize use of. Corticosteroids may interfere with accurate disease response assessment. High potency topical corticosteroids and systemic corticosteroids doses greater than 10mg prednisone daily or its equivalent are prohibited unless needed to treat adverse events. Effort should be made to taper steroids to the minimum required dose. Other anti-lymphoma therapies are prohibited including retinoic acids and phototherapy. Appendix C (Patient Clinical Trial Wallet Card) should be provided to patients if available.

6.4 Duration of Therapy

In the absence of treatment delays due to adverse event(s), treatment may continue for 12 cycles or until one of the following criteria applies:

- Disease progression. Patients randomized to the mogamulizumab-only arm may crossover as per section 6.6. Relapse in skin or blood compartments as defined by the response criteria is not considered progression and does not require removal from the treatment protocol.
- Intercurrent illness that prevents further administration of treatment
- Unacceptable adverse event(s)
- Patient decides to withdraw from the study
- General or specific changes in the patient's condition render the patient unacceptable for further treatment in the judgment of the investigator
- Clinical progression
- Patient non-compliance
- Pregnancy
 - All women of child bearing potential should be instructed to contact the investigator immediately if they suspect they might be pregnant (e.g., missed or late menstrual period) at any time during study participation.
 - The investigator must immediately notify CTEP in the event of a confirmed pregnancy in a patient participating in the study.
- Termination of the study by sponsor
- The drug manufacturer can no longer provide the study agent

The reason(s) for protocol therapy discontinuation, the reason(s) for study removal, and the corresponding dates must be documented in the Case Report Form (CRF).

6.5 Duration of Follow-Up

Patients will be followed for two years after their last treatment, until progression, or until the start of the next significant treatment, whichever occurs first. Patients removed from study for unacceptable adverse event(s) will be followed until resolution or stabilization of the adverse event.

